7.2.1 Primary Efficacy Criterion

The primary endpoint will be analysed as described in the clinical trial protocol (CTP).

The proportional hazards model will include planned treatment as explanatory variable, and have the proportional hazards assumptions checked by assessing whether or not the survival functions cross each other. The hazard ratio and corresponding 95% Wald confidence limits will be estimated within the proportional hazards model with planned treatment group as explanatory variable. A likelihood ratio test within the proportional hazards model will be applied for comparison of treatment groups. The results will be presented by treatment location (face/chest or scalp) and treatment group within treatment location as well as overall by treatment group (ingenol disoxate versus vehicle). The analysis will be based on the FAS.

The cumulative incidence rate will be calculated as the number of subjects with one or more events divided by the total observation period across all subjects in the FAS. The lower and upper limits of the 95% confidence interval will be calculated using the following SAS code:

Lower=((cinv(0.025,#subjects*2)/2)/total_obs_period)

Upper = ((cinv(0.975,2*(#subjects+1))/2)/total_obs_period)

The cumulative incidence rate and corresponding 95% confidence interval will also be presented by treatment location (face/chest or scalp) and treatment group within treatment location as well as overall by treatment group (ingenol disoxate versus vehicle).

For the landmark analysis described in the CTP time=0 will be defined as the date of visit 7 (week 8). This analysis will be based on the follow-up analysis set (FUAS) excluding subjects who experience an event prior to visit 7. Subjects in FUAS who do not have a visit 7, will have the date of their visit 7 imputed as the date of their visit 6 (week 4) plus 28 days.

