11.3.3 Exposure and Treatment Compliance

11.3.4 Analysis of Primary Endpoint

The null hypothesis is that there is no difference in time to first SCC between ingenol disoxate gel and vehicle gel. The hypothesis will be tested against the two-sided alternative that there is a difference between the two treatment groups.

Primary endpoint is time to first SCC in the treatment area from Visit 2 in trials LP0084-1193, -1194, -1195 and -1196.

Only the SCC confirmed by the IAC will be used in the primary endpoint analysis.

The annual and the 3-year and 2 months cumulative incidence of first event of SCC will be calculated for each treatment group (active and vehicle) in main trial using methods of survival analysis in the presence of censoring. The cumulative incidence rates will be presented by treatment group for the event of first SCC as primary endpoint. A proportional hazards model will be fitted if the model assumptions are valid. Log-rank test comparing the two treatment groups will be performed. For descriptive purposes, as an additional analysis, the difference in cumulative incidence rates between the two arms will be estimated and presented together with its 95% confidence interval. A landmark analysis will additionally be performed in order to exclude SCC and other neoplasia reported within the first 8 weeks which are not assumed to be associated with the trial treatment. This corresponds to left-truncation of the trial period at 8 weeks, the analysis will otherwise be conducted as above. Patients who experience a SCC before the 8-week landmark time point are excluded from the landmark analysis.

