- Kaplan-Meier curve for SCC (scalp): full analysis set
- Kaplan-Meier curve for SCC (landmark analysis, scalp): follow-up analysis set
- Kaplan-Meier curve for SCC: full analysis set
- Kaplan-Meier curve for SCC (landmark analysis): follow-up analysis set
- Kaplan-Meier curve for SCC or other skin neoplasia (face/chest): full analysis set
- Kaplan-Meier curve for SCC or other skin neoplasia (landmark analysis, face/chest): follow-up analysis set
- Kaplan-Meier curve for SCC or other skin neoplasia (scalp): full analysis set
- Kaplan-Meier curve for SCC or other skin neoplasia (landmark analysis, scalp): full analysis set

Trial ID: LP0084-1369	Date: 27-May-2018	Version: 1.0 Page 14 of 14
------------------------------	--------------------------	-------------------------------

- Kaplan-Meier curve for SCC or other skin neoplasia: full analysis set
- Kaplan-Meier curve for SCC or other skin neoplasia (landmark analysis): follow-up analysis set
- Onset of each SCC for face/chest (left panel) and scalp (right panel): follow-up analysis set
- Onset of each SCC or other skin neoplasia for face/chest (left panel) and scalp (right panel): follow-up analysis set

Listings

- Serious adverse events (week 8 - months 14 in main trials and LP0084-1369): follow-up analysis set

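### The only check of proportional hazards is whether the survival curves cross, which is not a valid check, and the protocol and SAP do not agree on whether it decides that the hazard ratio is reported.

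*SAP*

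**What the plan says.** Protocol 11.3.4 states: "A proportional hazards model will be fitted if the model assumptions are valid". The next sentence sets the test with no such condition: "Log-rank test comparing the two treatment groups will be performed". The same section also plans a descriptive difference in cumulative incidence with its 95% CI.

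SAP 7.2.1 begins by adopting the protocol analysis. It then has the "proportional hazards assumptions checked by assessing whether or not the survival functions cross each other". It does not say how large or lasting a crossing must be, over what period, or in which comparison. It names no residual, log-log or time-interaction diagnostic. The sentences that follow carry no condition: "The hazard ratio and corresponding 95% Wald confidence limits will be estimated within the proportional hazards model" and "A likelihood ratio test within the proportional hazards model will be applied for comparison of treatment groups".

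The analysis is repeated by location: "The results will be presented by treatment location (face/chest or scalp) and treatment group within treatment location". Appendix I lists matching figures, for example "Kaplan-Meier curve for SCC (scalp): full analysis set". SAP 7.2.2 extends the whole approach to the secondary endpoint, and SAP 7.4.1 expects few events and heavy censoring.

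**The concern.** Whether two survival curves cross and whether two hazards are proportional are different questions. If the treatment has no effect, the hazards are exactly proportional and the true curves coincide, so the estimated curves cross by chance. If an early effect fades to nothing, the hazards are clearly not proportional, yet the true curves never meet again after time zero. With few events, chance dominates what the plot shows.

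What is at stake is the reporting of the effect estimate. If the protocol's condition and the SAP's check are read together, a crossing removes the hazard ratio, its CI and the likelihood ratio test. If the SAP's unconditional sentences are read alone, the check has no consequence. Two analysts with the same data could therefore take opposite decisions. The trial was set up partly to answer concern about SCC after treatment (protocol 3.3), so its effect estimate should not hang on an undefined visual judgement.

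**Working it through.** **1. The plan's own figures.** Protocol 11.1 gives average upper 95% limits at 38-month risks of 4% and 6%. The formula p + 1.96·√(p(1−p)/n) reproduces all four:

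- p = 0.04, n = 800: 0.04 + 1.96 × 0.00693 = 5.36%
- p = 0.04, n = 400: 0.04 + 1.96 × 0.00980 = 5.92%
- p = 0.06, n = 800: 0.06 + 1.96 × 0.00840 = 7.65%
- p = 0.06, n = 400: 0.06 + 1.96 × 0.01187 = 8.33%

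These supply the risks used below. The plan gives no error rate for the crossing check.

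**2. True curves under a fading effect.** Take a constant vehicle hazard h, hazard ratio r up to month T, and 1 after that. The ratio of survival functions, active to vehicle, is exp{(1−r)·h·t} up to T and stays at exp{(1−r)·h·T}. For 4% risk, h = −ln(0.96)/38 = 0.001074 per month. With r = 0.4 and T = 14 the exponent is 0.6 × 0.001074 × 14 = 0.0090, so the ratio stays at about 1.009 from Month 14 on. It never returns to 1, so there is no crossing.

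**3. Inputs for estimated curves.** From the documents: 1234 subjects in the FAS (SAP 6.2), split 2:1 (about 823 and 411); 562 enrolled in the extension (SAP 6.1); the others censored at the end of the main trial, about Month 14 (SAP 7.4.1); vehicle risk 4–6% over 38 months (protocol 11.1). Assumed: constant vehicle hazard, 2% risk as a sensitivity case, and the follow-up after the early stop, which the documents do not give.

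- A: 10% lost before Month 14; extension follow-up uniform over 3–12 months (to Months 17–26)
- B: extension follow-up ends uniformly over Months 18–24 or 20–28
- C: extension follow-up ends uniformly over Months 20–33; 5% of those not continuing lost before Month 14

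The dates bound these. Extension entry was planned from Q2 2017, Visit 1 is no later than Visit 2, and Visit 2 is 6 months ±16 days after Visit 11 (protocol 6.2 and 8.1). Visit 11 is then no earlier than about mid-September 2016, some 20 months before the SAP date of 27 May 2018, so follow-up reaches at most about Month 14 + 20 = 34. If Visits 1 and 11 coincide it is about 14 + 14 = 28. C is therefore near the upper limit.

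**4. Proportion of simulated trials flagged as crossing** (1500–4000 trials per setting in A, 3000 in C):

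| Follow-up | Truth | Any sign change | 0.5-point gap each way |
|---|---|---|---|
| A, risk 2 / 4 / 6% | Proportional, HR 1 | 78 / 85 / 89% | 12 / 29 / 44% |
| A, risk 2–6% | Proportional, HR 0.5 | 65–71% | 4–13% |
| A, risk 2–6% | Fading, five patterns | 52–82% | 8–37% |
| B, risk 4–6% | Proportional, HR 1 | 83–89% | 22–44% |
| B, risk 4–6% | Fading | 65–70% | 11–19% |
| C, risk 4 / 6% | Proportional, HR 1 | 88 / 91% | 38 / 51% |
| C, risk 4 / 6% | Proportional, HR 0.5 | 71 / 69% | 12 / 15% |
| C, risk 4 / 6% | Fading | 73 / 73% | 25 / 31% |

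The patterns in A are HR 0.2, 0.3 or 0.5 returning to 1 at Month 6, and 0.2 or 0.3 returning at Month 12. In C it is HR 0.4 to Month 14, then 1. Mean events at HR 1 were about 11, 22 and 33 in A, and 26 and 38 in C. Under both rules in the table, every fading pattern was flagged less often than HR 1 at the same risk. The few exceptions arose under other definitions (a 1-point gap, or ignoring the first third of follow-up), with differences of at most 0.6 points.

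**5. If a crossing withholds the hazard ratio.** Median estimate given no crossing, over assumed windows of Months 18–24, 20–33 and 20–38. The last does not fit the dates in step 3, but the shorter windows lie inside the ranges.

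| Truth | All trials | Any sign change | 0.5-point gap |
|---|---|---|---|
| 0.5, overall | 0.50 | 0.36–0.41 | 0.45–0.49 |
| 2, overall | 2.00–2.04 | 2.28–2.48 | 2.11–2.19 |
| 0.5, one location | 0.49–0.50 | 0.30–0.33 | 0.41 |
| 2, one location | 2.04 | 2.63–3.11 | 2.36–2.52 |

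The location rows assume an equal split and Months 20–33.

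**The case against.** The best defence is that nothing need be withheld. SAP 7.2.1 says the hazard ratio will be estimated and the likelihood ratio test applied, and Appendix I lists the time-to-event tables without condition. On that reading there is no selective reporting and the main remedy is already planned. This stands as a reading, and a reader who infers that the SAP contains an explicit withholding rule goes further than its text. But the SAP also adopts protocol 11.3.4, which does contain a condition, so the conflict remains. For the same reason it would be too strong to say that the plan attaches no consequence to a failed check.

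A reader might also infer that the check largely misses a fading effect. The documents do not support this. They set no tolerance, and if any sign change counts, a fading effect is flagged in about half to four-fifths of trials. What holds is that the flag is no more frequent than under HR 1.

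Crossing does pick up some reversals: HR 0.4 to Month 8 and then 2.5 was flagged in 93–98% of trials on any sign change and 54–76% at a 0.5-point gap (same three windows as step 5). The opposite reversal was flagged in 65–84% and 24–61%, much nearer to the rates at HR 1.

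Finally, a residual-based test is no strong detector either. It keeps false flags near 4–7%, but its power against fading was only about 6–29%. That is a reason not to let any pre-test decide what is reported.

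**Conclusion.** The point holds for the validity of the check and for the unreconciled passages. Crossing flags exactly proportional hazards at HR 1 in about 78–91% of trials on any sign change and about 12–51% at a 0.5-point gap, and it does not separate a fading effect from HR 1. These rates rest on the assumed risks and follow-up in step 3, since the documents give no event counts. The argument about the true curves needs no such assumption.

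The harm is confined to reporting of the effect estimate, and it arises only if a crossing withholds it. The exaggeration is then marked if any sign change counts, slight overall at a 0.5-point gap, and larger within location. It would be wrong to infer that the trial's test is compromised: the log-rank test, cumulative incidence difference, incidence rates, Kaplan-Meier curves and type I error do not depend on the check.

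**What to change.** In SAP 7.2.1, delete crossing as a condition for fitting or reporting the model, and say how this relates to the condition in protocol 11.3.4. Protocol 11.3.8 allows such a change to be described and justified in the SAP update. State that the Cox hazard ratio and its 95% CI are reported in all cases, overall and by location, for the primary and secondary endpoints.

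Show scaled Schoenfeld residuals or a treatment-by-time term as descriptive support, note the low power with few events, and state that the result does not change what is reported. Interpret the hazard ratio alongside the cumulative incidence difference already planned.

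The cost is SAP wording and minor programming, with no new data. The downside is that, when hazards are not proportional, the reported hazard ratio is only an average effect and should be described as such.

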11.1 Sample Size

No formal sample size calculation has been made. The sample size is determined by the number of subjects who complete Visit 11 in the pivotal phase 3 trials (LP0084-1193, -1194, -1195, -1196) and are willing to enter the extension protocol. Two thirds have been treated with ingenol disoxate, one third with vehicle.

A total of 1200 subjects were planned be enrolled in the pivotal phase 3 trials (LP0084-1193, -1194, -1195, and -1196) and randomised 2:1 to the two treatment groups ingenol disoxate gel or vehicle gel. With 800 subjects in the ingenol disoxate treatment group and 400 subjects in the vehicle gel group, an adequate precision of the 3-year plus 2 months incidence rate can be obtained. Assuming a 3-year plus 2 months rate of 4.0%, the upper 95% confidence limit will on average be 5.36% for ingenol disoxate gel and 5.92% for vehicle gel, and assuming a 6.0% rate, the upper 95% confidence limit will on average be 7.65% for ingenol disoxate gel and 8.33% for vehicle gel.

Trial ID: LP0084-1369	Date: 25-Jul-2017	Version: 2.0 Page 24 of 52
-----------------------	-------------------	-------------------------------

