11.3.8 General Principles

All significance tests will be two-sided using the 5% significance level. All confidence intervals will be presented with 95% degree of confidence.

An observed-cases approach will be used for tabulations of data by visit (i.e. involving only those subjects who attended each specific visit).

Categorical data will be summarised using the number and percentage of subjects in each category. Continuous data will be summarised using the mean, median, standard deviation (SD), minimum and maximum values.

Trial ID: LP0084-1369	Date: 25-Jul-2017	Version: 2.0 Page 28 of 52
-----------------------	-------------------	-------------------------------

Any changes from the statistical analysis planned in this clinical trial protocol will be described and justified in a protocol amendment/the statistical analysis plan update and/or in the clinical trial report dependent on the type of deviation.

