7.2.2 Secondary Efficacy Criteria

The secondary endpoint will be analysed as described in the CTP and above for the primary endpoint.

Trial ID: LP0084-1369	Date: 27-May-2018	Version: 1.0 Page 9 of 14
-----------------------	-------------------	------------------------------

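### SAP 7.2.1 calls a person-time rate without a unit the cumulative incidence rate, and neither document says how the between-arm difference in cumulative incidence is to be estimated

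*SAP*

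**What the plan says.** Protocol 11.3.4 states: "The annual and the 3-year and 2 months cumulative incidence of first event of SCC will be calculated for each treatment group". It asks for survival methods that allow for censoring. It then uses a second term for the same results, "The cumulative incidence rates will be presented by treatment group for the event of first SCC as primary endpoint", and adds as a descriptive analysis that "the difference in cumulative incidence rates between the two arms will be estimated and presented together with its 95% confidence interval". It names neither an estimator nor an interval method. Protocol 11.1 gives the planned precision: "Assuming a 3-year plus 2 months rate of 4.0%, the upper 95% confidence limit will on average be 5.36" percent in the active arm, with matching figures for vehicle and for a 6.0% rate.

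SAP 7.2.1 opens with "The primary endpoint will be analysed as described in the clinical trial protocol (CTP". Later in the same section it says: "The cumulative incidence rate will be calculated as the number of subjects with one or more events divided by the total observation period", summed over the FAS, and gives chi-square (exact Poisson) limits as SAS code. No time unit appears. SAP 7.2.2 extends this: "The secondary endpoint will be analysed as described in the CTP and above for the primary endpoint".

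SAP Appendix I lists time-to-event tables and incidence tables as separate outputs, and Kaplan-Meier curves as figures. No table title names the between-arm difference, and no read-off times are given for the curves.

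**The concern.** A cumulative incidence is the probability of an event by a stated time. An events-per-person-time quantity is a rate, and its value depends on the unit. The SAP gives the rate the protocol's name for the probability, so the term has two meanings across the two documents. The protocol's difference in cumulative incidence rates can then be read as a rate difference or as a risk difference at a fixed time.

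The primary objective is to compare SCC incidence, and this is the absolute measure that would be reported for it. A reader could take the SAP figure for the protocol's 12-month or 38-month risk, or set it against the 4% and 6% planning values, with which it is not comparable.

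Follow-up is also unequal. The FAS has 1234 subjects (SAP 6.2), of whom 562 entered the extension (SAP 6.1), which is 562/1234 = 46%. Completers of the main trials who did not enter are censored there (SAP 7.4.1), and the trial stopped early (SAP 5). Person-time is therefore weighted towards the first 14 months.

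**Working it through.** **1. What the protocol's planning figure is.** Inputs from protocol 11.1: p = 0.04 or 0.06, n = 800 or 400. The Wald upper limit for a proportion is p + 1.96·√(p(1−p)/n).

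| p | n | Computed | Protocol |
|---|---|---|---|
| 0.04 | 800 | 5.36% | 5.36% |
| 0.04 | 400 | 5.92% | 5.92% |
| 0.06 | 800 | 7.65% | 7.65% |
| 0.06 | 400 | 8.33% | 8.33% |

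All four reproduce, so the planned quantity is a proportion at 38 months.

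**2. The same risk as a rate (constant hazard assumed).** λ = −ln(1−p)/38 per month; 12-month risk = 1 − exp(−12λ).

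| 38-month risk | Per 100 person-years (1200λ) | Per 100 person-months (100λ) | 12-month risk |
|---|---|---|---|
| 4% | 1.29 | 0.107 | 1.28% |
| 6% | 1.95 | 0.163 | 1.93% |

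The printed value changes twelvefold with the unit. In person-years it is close to the annual risk.

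**3. The SAP formula at the planning sizes.** Assume follow-up to 38 months with time stopped at first event. Events D = np; person-years = n(1 − exp(−38λ))/(12λ); upper limit = χ²(0.975; 2(D+1))/2 ÷ person-years.

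| p | n | D | Person-years | Upper limit per 100 person-years |
|---|---|---|---|---|
| 0.04 | 800 | 32 | 2482 | 1.82 |
| 0.04 | 400 | 16 | 1241 | 2.09 |
| 0.06 | 800 | 48 | 2457 | 2.59 |
| 0.06 | 400 | 24 | 1228 | 2.91 |

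If everyone instead contributes a full 38 months, the limits are 1.78, 2.05, 2.51 and 2.82. The SAP does not say which rule applies.

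**4. What the difference could mean.** For an illustrative 4% versus 6% contrast:
- Rate difference: 1.954 − 1.289 = 0.66 per 100 person-years.
- 12-month risk difference: 1.935 − 1.281 = 0.65 percentage points.
- 38-month risk difference: 2.0 percentage points.

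**5. Whether the rate can stand in for a risk.** Assume 14 months for all 1234, 24 more for 562, and a hazard that changes at month 14 (h1 before, h2 after, per 100 person-years). Each row gives the same overall rate of 1.29. The 38-month risk is 1 − exp(−(h1·14/12 + h2·2)/100).

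| h1 | h2 | Events / person-years | 12-month risk | 38-month risk |
|---|---|---|---|---|
| 0.64 | 2.14 | (9.2+23.4)/(1434+1092) | 0.64% | 4.9% |
| 1.29 | 1.29 | constant hazard | 1.28% | 4.0% |
| 1.93 | 0.45 | (27.5+4.9)/(1424+1094) | 1.92% | 3.1% |

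One rate is compatible with quite different risks, so it cannot replace the fixed-time estimate.

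**6. Whether 38 months is reachable.** The planned first visit was Q2 2017 (protocol 6.2). Visit 1 is due no later than Visit 2, which falls 6 months ± 16 days after month 14 (protocol 8.1), so a subject is at about month 20.5 at most on entry. From 1 April 2017 to the SAP date of 27 May 2018 is just under 14 months, giving about 34.5 months at most. This uses planned dates only.

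**7. Precision of a risk difference.** Assume a 2:1 split, equal constant hazards, and no loss before month 14. Variance = sum over arms of S(t)²·[(exp(λ·min(t,14)) − 1)/(aN) + (exp(λ·max(t−14,0)) − 1)/(a·562)], with a = 2/3 and 1/3, and N = 1234 (FAS) or 1172 (follow-up set, SAP 6.4). Example for 12 months, p = 0.04, N = 1234: 0.01281·0.98719·(1/822.7 + 1/411.3) = 4.61×10⁻⁵, so the half-width is 1.96·√(4.61×10⁻⁵) = 1.33 points.

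| Planning risk | N | 12 months | 24 months |
|---|---|---|---|
| 4% | 1234 | 1.33 | 2.27 |
| 4% | 1172 | 1.37 | 2.30 |
| 6% | 1234 | 1.63 | 2.77 |
| 6% | 1172 | 1.67 | 2.80 |

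The 24-month values are a floor, because they assume that all 562 entrants reach that time.

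**The case against.** The strongest reply is that nothing has been lost. SAP 7.2.1 carries the protocol analysis over by reference, SAP 7.4.1 repeats that the survival analyses allow for censoring, and Appendix I separates time-to-event tables from incidence tables. On that reading the person-time rate is a supplement for the incidence tables, and the fixed-time estimates sit in the other tables, whose contents are not shown. This stands in part. A reader might infer that the SAP formula overrides or drops the protocol's cumulative incidence, but no document sets an order of precedence and the reference keeps the protocol analysis alive. It does not remove the conflict: the rate still carries the protocol's term, and no method for the difference appears anywhere.

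A reader might also set 1.82 against 5.36% as the size of an error. That is mostly a change of unit. Converted to 38-month risk under the same constant hazard, the four limits in step 3 become 5.60%, 6.41%, 7.88% and 8.80%, against 5.36%, 5.92%, 7.65% and 8.33%. The remaining gap largely reflects exact Poisson versus Wald limits.

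Nor do the documents show that a change was concealed. SAP 7.1.1 and 7.3.1 explain other departures and this one is not flagged. But the protocol rule, "Any changes from the statistical analysis planned in this clinical trial protocol will be described and justified", also accepts the trial report as the place, and that report is not available here.

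Finally, the 2.0-point contrast at 38 months probably could not be observed (step 6). That loss comes from the early stop, not from the formula.

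**Conclusion.** The point holds as a fault of naming and specification. SAP 7.2.1 attaches the protocol's term to a person-time rate without a unit. Kaplan-Meier cumulative incidence can be inferred but contradicts the only written formula, and the between-arm difference and its interval have no method in either document. SAP 7.2.2 carries the fault to the secondary endpoint.

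The size is modest. In person-years and under a constant hazard the rate nearly equals the annual risk (1.29 against 1.28%). It does not give a later risk, and if the hazard changes it can miss the annual risk too (0.64% to 1.92% in step 5). The log-rank test, hazard ratio and Kaplan-Meier curves do not depend on it, and the protocol presents the difference as descriptive.

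The documents give no event counts or achieved follow-up. The conversions, hazard patterns and half-widths therefore rest on the stated assumptions. The naming conflict does not.

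**What to change.** In SAP 7.2.1:

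- Rename the quantity *incidence rate per 100 person-years*. Use each group's own events and own time at risk, stopped at first event or censoring. State that the subject count in the SAS code means subjects with an event, and how the lower limit is set when there are none (the code then has zero degrees of freedom).
- Define cumulative incidence as 1 minus Kaplan-Meier by arm at 12 months and at one later time. Because 38 months is unlikely to be reached, set the later time by a numbers-at-risk rule that applies to both arms and is written in the SAP before analysis. The documents give no basis for a particular threshold. The sponsor should choose it from the precision it needs, without reference to event counts by arm.
- Give a 95% interval for each arm on the log-log scale, since events are expected to be few. Give the between-arm difference with a 95% interval from Greenwood variances, and show numbers at risk. In a location-by-arm cell with no events the Greenwood variance is zero, so say in advance how that case is shown.
- Apply the same to the secondary endpoint, and record the change from protocol 11.3.4.

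The cost is SAP wording and a few lines of code. The curves are already planned, so no new data are needed. The downside is imprecision at the later time: a half-width of at least 2.27 to 2.80 points at 24 months under the assumptions in step 7.
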